6.2.2 Serious Adverse Event

The terms "severe" and "serious" are not synonymous. Severity (or intensity) refers to the grade of an AE (see below). "Serious" is a regulatory definition and is based on subject or event outcome or action criteria usually associated with events that pose a threat to a subject's life or functioning. Seriousness (not severity) serves as the guide for defining regulatory reporting obligations from the sponsor to applicable regulatory authorities.

An AE should be classified as an SAE if it meets any 1 of the following criteria:

- It results in death (i.e., the AE actually causes or leads to death)
- It is life-threatening (i.e., the AE, in the view of the investigator, places the subject at immediate risk of death at the time of the event. It does not include an AE that, had it occurred in a more severe form, might have hypothetically caused death)
- It requires or prolongs inpatient hospitalization
- It results in persistent or significant disability/incapacity (i.e., the AE results in substantial disruption of the subject's ability to conduct normal life functions)
- It results in a congenital anomaly/birth defect in a neonate/infant born to a mother exposed to the investigational product
- It is considered a significant medical event by the investigator based on medical judgment (e.g., may jeopardize the subject or may require medical/surgical intervention to prevent one of the outcomes listed above)

6.2.3 Adverse Events of Special Interest

The following events are adverse events of special interest (AESIs) for subjects randomized to the acalabrutinib-containing combinations arm and must be reported to the Sponsor expeditiously (see Section 6.3.5 for reporting instructions), irrespective of regulatory seriousness criteria or causality.

 Ventricular arrhythmias (e.g., ventricular extrasystoles, ventricular tachycardia, ventricular arrhythmia, ventricular fibrillation)

For study treatment containing biologic products:

 Suspected transmission of an infectious agent by the study drug whereby any organism, virus, or infectious particle (e.g., prion protein transmitting transmissible spongiform encephalopathy), pathogenic or non-pathogenic is

considered an infectious agent. A transmission of an infectious agent may be suspected from clinical symptoms or laboratory findings indicating an infection in a subject exposed to a medicinal product. This term ONLY applies when a contamination of the study drug is suspected, NOT for infections supported by the mode of action, e.g., immunosuppression.

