3 STUDY DESIGN

3.1 DESCRIPTION OF STUDY

This study will be conducted in 3 parts. Note: Text throughout the protocol applies to all parts of the study unless otherwise specified. At the time of Amendment 6, the sponsor made the decision to close Part 4 of the study (R/R DLBCL: Acalabrutinib + rituximab and lenalidomide).

Part 1

This part of the study is a Phase 1b, multicenter, open-label, randomized, parallel group study to be conducted at approximately 11 centers. Two cohorts will be

enrolled in parallel: The Relapsed/Refractory Cohort will include approximately 24 subjects with R/R FL, and the Treatment-Naive Cohort will include 12 subjects who have not previously been treated for FL. Note: At the time of Amendment 4, enrollment in Part 1 has been completed.

Arm 1: Acalabrutinib 100 mg by mouth (PO) BID administered approximately 12 hours apart (BID dosing=200 mg total daily dose) for 28 days

Arm 2: Acalabrutinib 100 mg PO BID administered approximately 12 hours apart (BID dosing=200 mg total daily dose) for 28 days, plus rituximab 375 mg/m² intravenous (IV) on Days 1, 8, 15, and 22 of Cycle 1 and Day 1 of Cycles 2 through 6

Treatment-Naive Cohort: A total of 12 subjects will receive the combination of acalabrutinib and rituximab: acalabrutinib 100 mg PO BID administered approximately 12 hours apart (BID dosing=200 mg total daily dose) for 28 days, plus rituximab 375 mg/m² IV on Days 1, 8, 15, and 22 of Cycle 1 and Day 1 of Cycles 2 through 6.

PK/PD testing will be performed in Cycle 1 and Cycle 2. Tumor assessments will be performed at 8- to 24-week intervals during the trial. Refer to Appendix 4 for a comprehensive list of study assessments and their timing.

Part 2

[figure not shown]
This part of the study is a Phase 2, multicenter, open-label, study to be conducted at approximately 38 centers. Up to 40 subjects with R/R MZL will be enrolled. Each cycle is 28 days. At the time of Amendment 6, the decision was made to close Cohort 2.

Cohort 1: Acalabrutinib 100 mg PO BID administered approximately 12 hours apart (BID dosing=200 mg total daily dose) for 28 days

Cohort 2: Acalabrutinib 100 mg PO BID administered approximately 12 hours apart (BID dosing=200 mg total daily dose) for 28 days, plus rituximab 375 mg/m² IV on Days 1, 8, 15, and 22 of Cycle 1 and Day 1 of Cycles 2 through 6.

The study schema for Part 2 of the study is presented in Figure 1.

Figure 1 Part 2 Study Schema

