5.2 SAMPLE SIZE CONSIDERATIONS

Part 1

This study will assess acalabrutinib safety, PK, PD, and antitumor activity when administered alone or in combination with rituximab. A total of 24 subjects (12 each arm) in the Relapsed/Refractory Cohort will be equally randomized into 1 of 2 treatment arms (monotherapy and combination therapy). Twelve subjects will be enrolled to the Treatment-naive Cohort receiving the combination therapy. The study is not formally designed to compare these regimens but rather to obtain descriptive information that can be used in support of further acalabrutinib development.

The primary objective of this study is to determine the safety as such:

- With a total sample size of 36, the probability of observing one or more instances
 of an AE with a background rate of 5% and 10% is 84% and 98%, respectively.
- For each treatment arm (n=12 each), the probability of observing one or more instances of an AE with a background rate of 5% and 10% is 46% and 72%, respectively.
- This provides reasonable assurance for generating preliminary safety data for this Phase 1b, proof-of-concept study.

Part 2

Part 2 will enroll up to 40 subjects in Cohort 1. The primary objective is to characterize the activity of acalabrutinib alone in subjects with R/R MZL as measured by the ORR. Up to 40 subjects in treatment Cohort 1 will provide data for an initial assessment of safety and efficacy of acalabrutinib treatment. Sample size is not based on statistical power consideration.

Part 3

A total of approximately 26 to 32 subjects are to be enrolled in Part 3. This sample size will provide adequate data for an initial assessment of safety and efficacy of acalabrutinib treatment in combination with lenalidomide and rituximab. This sample size is not based on statistical power consideration.

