All SAEs and AESIs must be reported within 24 hours of discovery. Initial SAE/AESI reports and follow-up information will be reported using the protocol-specific electronic data capture system according to the investigator site file. If electronic SAE reporting is not available, paper SAE/AESI forms must be completed and emailed or faxed to the

Sponsor's Drug Safety department, or designee. The Sponsor may request follow-up and other additional information from the investigator (e.g., hospital admission/discharge notes and laboratory results). After final database lock, new or follow-up to existing SAEs will be reported using a paper form.

Whenever possible, AEs/SAEs should be reported by diagnosis term not as a constellation of symptoms.

Death due to disease progression should be recorded on the appropriate form in the EDC system. If the primary cause of death is disease progression, then the death due to disease progression should not be reported as an SAE. If the primary cause of death is something other than disease progression, then the death should be reported as an SAE with the primary cause of death as the event AE term, as death is typically the outcome of the event, not the event itself. The primary cause of death on the autopsy report should be the term reported. Autopsy and postmortem reports must be forwarded to the Sponsor's Drug Safety department, or designee, as outlined above.

If study drug is discontinued because of an SAE, this information must be included in the SAE report.

An SAE may qualify for mandatory expedited reporting to regulatory authorities if the SAE is attributable to the investigational product and is not listed in the current Investigator's Brochure (i.e., an unexpected event). In this case, the Sponsor's Drug Safety department or designee will forward a formal notification describing the Suspected Unexpected Serious Adverse Reaction (SUSAR) to all investigators. Each investigator must then notify his or her IRB/IEC of the SUSAR.

	Drug Safety Contact Information
	[contact] (United States)
[contact] (for outside the United
	States)
Email:	[contact]

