# 3.2 Sample Size

#### Part 2

Part 2 will enroll up to 40 subjects in Cohort 1 that will provide data for an initial assessment of safety and efficacy of acalabrutinib treatment. Sample size is not based on statistical power consideration. At the time of CSP Amendment 6, the decision was made to close Cohort 2 (per CSP Amendment 4, Cohorts 1 and 2 were planned to enroll 20 subjects each). One subject was enrolled in Cohort 2 before it was closed.

#### Part 3

A total of approximately 26 to 32 subjects are to be enrolled in Part 3. This sample size will provide adequate data for an initial assessment of safety and efficacy of acalabrutinib treatment in combination with lenalidomide and rituximab. This sample size is not based on statistical power consideration.

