# 7.7.2 Adverse Events of Special Interest (AESIs) and Events of Clinical Interest (ECIs)

AESIs and ECIs are defined in Appendix 1. Subject incidence will be presented by treatment arm in the summary tables.

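### The AESI definition in Protocol 6.2.3 is worded for a randomized combination arm, so most subjects here fall outside 24-hour reporting of non-serious ventricular arrhythmias

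*Protocol*

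**What the plan says.** Protocol Section 6.2.3 names ventricular arrhythmias as AESIs "for subjects randomized to the acalabrutinib-containing combinations arm and must be reported to the Sponsor expeditiously", whatever their seriousness or causality. It adds a second item, suspected transmission of an infectious agent, for study treatment that contains a biologic product.

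The reporting duty is set elsewhere. Section 6.3.5 states: "All SAEs and AESIs must be reported within 24 hours of discovery". Section 6.3.1 sets the same 24-hour limit. Neither names an arm or a part, and neither defines an AESI.

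On allocation, Protocol Section 5.2 says of Part 1: "A total of 24 subjects (12 each arm) in the Relapsed/Refractory Cohort will be equally randomized into 1 of 2 treatment arms". For the untreated patients it says: "Twelve subjects will be enrolled to the Treatment-naive Cohort receiving the combination therapy". Section 3.1 introduces Part 2 with "This part of the study is a Phase 2, multicenter, open-label, study to be conducted at" about 38 centers, and describes no randomization in Part 2 or Part 3.

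The SAP for Parts 2 and 3 lists ventricular arrhythmias as an AESI in Appendix 1, by seven MedDRA preferred terms. Its only restriction, a footnote on biologic products, belongs to the infectious-agent category. On analysis, SAP Section 7.7.2 says: "Subject incidence will be presented by treatment arm in the summary tables".

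**The concern.** The purpose of an AESI is to bring an event to the sponsor quickly even when it meets no seriousness criterion. A definition tied to one randomized arm switches that off for everyone else. In a mostly non-randomized study, that is most of the subjects, including the largest cohort (Part 2 Cohort 1, acalabrutinib alone).

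The documents give no reason to limit the arrhythmia concern to combinations. SAP Appendix 1 also lists ventricular tachyarrhythmias as an event of clinical interest, and attributes these events to findings with acalabrutinib and to the pharmacology of approved BTK inhibitors.

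What is at stake is timeliness and follow-up detail. The investigator calls in Protocol Section 3.10 cover adverse events leading to dose modification, related SAEs and deaths. A non-serious ventricular arrhythmia without a dose change is not on that list. SAP Appendix 2 asks for a narrative for every AESI, and an expedited report with its follow-up would be a natural source for one.

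**Working it through.** The plan states no figure that depends on this scope, so the check is a headcount of planned subjects against the wording.

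**Inputs**
- Part 1 Arm 1 (monotherapy, randomized): 12 (Protocol 5.2).
- Part 1 Arm 2 (combination, randomized): 12 (Protocol 5.2).
- Part 1 Treatment-Naive Cohort (combination, enrolled directly): 12 (Protocol 5.2).
- Part 2 Cohort 1 (monotherapy): 40, from "Part 2 will enroll up to 40 subjects in Cohort 1".
- Part 2 Cohort 2 (combination): 1, from SAP 3.2, "One subject was enrolled in Cohort 2 before it was closed".
- Part 3 (triplet): 26 to 32 (Protocol 5.2).

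**Total**
- 12 + 12 + 12 + 40 + 1 + 26 = 103.
- 12 + 12 + 12 + 40 + 1 + 32 = 109.

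**Literal reading: randomized, and to a combination**
- Covered: Part 1 Arm 2 only, 12. This is 12/103 = 11.7% to 12/109 = 11.0%.
- Not covered: 103 − 12 = 91 to 109 − 12 = 97. By group: 12 (Arm 1) + 12 (treatment-naive) + 41 (Part 2) + 26 to 32 (Part 3).
- Covered in Parts 2 and 3: 0 of 67 to 73 (41 + 26 to 41 + 32).

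**Generous reading: randomized taken to mean enrolled**
- Covered: 12 + 12 + 1 + 26 to 32 = 51 to 57.
- Not covered: all monotherapy, 12 + 40 = 52. This is 52/103 = 50.5% to 52/109 = 47.7%, about half of the study.
- This reading also strains the protocol's usage, since the all-treated definition in Section 5.3 names randomized and enrolled subjects as alternatives.

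**What is lost for a subject outside the definition**
- Serious ventricular arrhythmia: nothing. Section 6.3.5 applies to all SAEs, and Section 6.2.2 lets the investigator class an event as serious on medical judgment.
- Non-serious ventricular arrhythmia, 24-hour notice: lost. Sections 6.3.1 and 6.3.5 depend on Section 6.2.3 for what counts as an AESI.
- Non-serious ventricular arrhythmia, data record: kept. Section 6.3.2 puts all AEs on the eCRF in every part.
- SAP incidence: kept. SAP Section 7.7 analyses treatment-emergent AEs, and Appendix 1 finds AESIs by preferred term, not from expedited reports.

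**The case against.** The best defence is that the phrase is leftover or borrowed wording and that the intended scope is wide. Section 3.1 says protocol text applies to all parts unless otherwise specified. The 24-hour rules carry no arm limit. Within Section 6.2.3 itself, the infectious-agent item is qualified as applying to treatment with a biologic. Every combination in this study contains rituximab, so that qualifier does something only if the AESI list also reaches monotherapy subjects. This is good evidence of intent, and it makes the problem an inconsistency. A reader might infer a deliberate decision to exclude monotherapy; the documents do not support that. Intent does not repair the text, however. Section 6.2.3 supplies the only protocol definition, and a site that follows it has no 24-hour duty for these events outside Part 1 Arm 2.

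Two further inferences are tempting and wrong. One is that ventricular arrhythmia escapes expedited reporting altogether. It does not, because serious events are covered in every arm. The other is that AESI incidence in the Parts 2-3 tables would be undercounted. It would not, because those tables draw on AEs recorded for all subjects.

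It is also fair to say that planned headcount is not a count of subjects still exposed to the gap. Part 1 enrollment was complete at Amendment 4. Section 3.2 puts the final cut-off at about 25 August 2023, and Section 6.3.1 stops AE reporting after it, leaving only SAEs. The sponsor also reviews AEs internally on an ongoing basis (Section 3.10).

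**Conclusion.** The scope phrase in Section 6.2.3 does not fit the design, and it conflicts with Sections 6.3.1 and 6.3.5 and SAP Appendix 1. Read literally it leaves out 91 to 97 of 103 to 109 subjects; on the most generous reading, up to 52. The consequence is confined to prompt notification, and the follow-up it triggers, for non-serious ventricular arrhythmias. Sample size, efficacy analyses and SAP incidence tables are unaffected.

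The counts assume that planned sizes are met, that Part 2 Cohort 1 reaches its ceiling of 40, and that all planned subjects receive study drug. The documents do not show how sites applied the rule or how many such events occurred, so the number of reports actually missed is unknown and may be zero. The point merits correction because a stated safety rule contradicts the rest of the documents and the repair is simple.

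**What to change.** In Protocol Section 6.2.3, replace the scope phrase with *for all subjects receiving acalabrutinib, alone or in combination*, and keep the infectious-agent item for subjects receiving a biologic product. This brings the definition into line with Sections 6.3.1 and 6.3.5 and with SAP Appendix 1; the SAP needs no change.

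If the final data cut-off has passed, an amendment cannot recover earlier notifications. The sponsor should then confirm which scope sites used and state it in the CSR, so that readers of the AESI narratives know whether non-serious events were reported promptly.

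The cost is one sentence of protocol text and a few more expedited reports of non-serious events, or a short statement in the CSR.

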6.2.4 Severity

Definitions found in the CTCAE (Version 4.03 for Part 1 and Version 5.0 for Parts 2 and 3) will be used for grading the severity (intensity) of AEs. The CTCAE displays Grades 1 through 5 with unique clinical descriptions of severity for each referenced AE. Should a subject experience any AE not listed in the CTCAE, the following grading system should be used to assess severity:

- Grade 1 (Mild AE) experiences that are usually transient, requiring no special treatment, and not interfering with the subject's daily activities
- Grade 2 (Moderate AE) experiences that introduce some level of inconvenience or concern to the subject, and which may interfere with daily activities, but are usually ameliorated by simple therapeutic measures
- Grade 3 (Severe AE) experiences that are unacceptable or intolerable, significantly interrupt the subject's usual daily activities, and require systemic drug therapy or other treatment
- Grade 4 (Life-threatening or disabling AE) experiences that cause the subject to be in imminent danger of death
- Grade 5 (Death due to AE) experiences that result in subject death

6.3 DOCUMENTING AND REPORTING OF ADVERSE AND SERIOUS ADVERSE EVENTS

The investigator is responsible for ensuring that all AEs and SAEs that are observed or reported during the study, as outlined in the prior sections, are recorded on the eCRF. All SAEs also must be reported using the SAE report form (see Section 6.3.5).

All SAEs, overdoses, and pregnancies must continue to be reported after the final data cut-off. Follow-up to existing SAEs must be entered in the clinical database. AEs will no longer be reported in the clinical database after final data cut-off but will instead be recorded in the subject's medical record. After database lock, all new or follow-up to existing SAEs and pregnancies must be reported on the SAE paper form.

6.3.1 Adverse Event Reporting Period

AEs and SAEs will be collected by the site from time of signature of ICF throughout the treatment period and including the follow-up period. After the signing of the ICF and prior to the first dose of study drug, all SAEs, regardless of causality, must be reported to the Sponsor.

All AEs and SAEs will be reported from first dose of study treatment until 30 days after the last dose of study drug(s) or the start of new anticancer therapy (whichever comes first). After this period, investigators should report SAEs that are believed to be related to the study drug(s) or any AEs of concern (deemed by the Sponsor or investigator), regardless of causality to the study drug(s) as relevant.

All SAEs that occur during the reporting period should be followed to resolution or until the investigator assesses the subject as stable or the subject is lost to follow-up or withdraws consent. Resolution/stable means the subject has returned to baseline state of health or the investigator does not expect any further improvement or worsening of the event.

All SAEs/AESIs will be recorded and reported to the sponsor or designee within 24 hours. The investigator will submit any updated SAE/AESI data to the sponsor within 24 hours of it being available.

Investigators are not obligated to actively seek AE or SAE data in former study subjects. However, if at any time after a subject's last visit the investigator learns of any SAE, including a death, that is considered to be reasonably related to the study treatment or study participation, the investigator may notify the Sponsor.

After the final DCO, the study will transition to the PTAP. Patients will be managed as per standard of care. All SAEs, irrespective of attribution of causality, will be collected and recorded in the subject's medical records. SAEs will be reported to the sponsor using a paper form via Fax or email. No AEs will be reported during the PTAP phase of the study.

6.3.2 Assessment of Adverse Events

Investigators will assess the occurrence of AEs and SAEs at all subject evaluation timepoints during the study. All AEs and SAEs whether volunteered by the subject, discovered by study personnel during questioning, or detected through physical examination, or other means will be recorded in the subject's medical record and on the AE eCRF.

Disease progression itself is not considered an AE; however, signs and symptoms of disease progression may be recorded as AEs or SAEs.

Each recorded AE or SAE will be described by its diagnostic term, duration (i.e., start and end dates), severity, regulatory seriousness criteria, if applicable, suspected relationship to the study drug (see following guidance), and any actions taken in regard to the event. The causal relationship of AEs to the study drug will be assessed by means of the question: "Is there a reasonable possibility that the event may have been caused by the study drug?" per FDA guidance on safety reporting requirements (FDA Safety Reporting Requirements for INDs and BA/BE Studies (December 2012)).

See Appendix 2 for more detail on assessing causality.

6.3.3 Second Primary Malignancies

AEs for malignant tumors reported during a study should generally be assessed as SAEs. If no other seriousness criteria apply, the "Important Medical Event" criterion should be used. In certain situations, however, medical judgment on an individual event basis should be applied to clarify that the malignant tumor event should be assessed and reported as a nonserious AE. For example, if the tumor is included as medical history and progression occurs during the study but the progression does not change treatment and/or prognosis of the malignant tumor, the AE may not fulfill the attributes for being assessed as serious, although reporting of the progression of the malignant tumor as an AE is valid and should occur. Also, some types of malignant tumors, which do not spread remotely after a routine treatment that does not require hospitalization, may be assessed as nonserious; examples in adults include Stage 1 basal cell carcinoma and Stage 1A1 cervical cancer removed via cone biopsy.

The above instruction applies only when the malignant tumor event in question is a new malignant tumor (i.e., it is not the tumor for which entry into the study is a criterion and that is being treated by the investigational product (IP) under study and is not the development of new or progression of existing metastasis to the tumor under study). Malignant tumors that—as part of normal, if rare, progression—undergo transformation (e.g., Richter's transformation of B-cell chronic lymphocytic leukemia into DLBCL) should not be considered a new malignant tumor.

